#### Evaluation of Non-Target Lesions

Complete Response (CR):	Disappearance of all non-target lesions and normalization of tumor marker level. All lymph nodes must be non-pathological in size (<10mm short axis).
Non-CR/Non-PD	Persistence of one or more non-target lesion(s) and/or maintenance of tumor marker level above the normal limits.

Progressive Disease (PD):	Unequivocal progression of existing non-target lesions. (Note: the appearance of one or more new lesions is also considered progression).
	Although a clear progression of “non-target” lesions only is exceptional, in such circumstances the opinion of the investigator will prevail.
*Note: If tumor markers are initially above the upper normal limit, they must normalize for a patient to be considered in complete clinical response.	

### Evaluation of Best Overall Response

The best overall response is the best response recorded from the start of the treatment until disease progression/recurrence (taking as reference for progressive disease the smallest measurements recorded since the treatment started). The patient's best response assignment will depend on the achievement of both measurement and confirmation criteria.

Target Lesions	Non-Target Lesions	New Lesions	Overall Response
CR	CR	No	CR
CR	Incomplete response/SD	No	PR
PR	Non-PD	No	PR
SD	Non-PD	No	SD
PD	Any	Yes or No	PD
Any	PD	Yes or No	PD
Any	Any	Yes	PD

Notes:

Patients with a global deterioration of health status requiring discontinuation of treatment without objective evidence of disease progression at that time should be classified as having "symptomatic deterioration." Every effort will be made to document the objective progression.

In some circumstances, it may be difficult to distinguish residual disease from normal tissue. When the evaluation of complete response depends on this determination, the residual lesion will be investigated (fine needle aspirate/biopsy if possible) before confirming the complete response status.

### **Modified RECIST**

Note on modified RECIST: In this particular study, RECIST criteria are modified with a stipulation that PD must be confirmed to account for pseudoprogression (tumor flare phenomenon). The first instance of PD must be confirmed by either:

- 1) confirmation of disease progression by repeat assessment 4-12 weeks later, and/or
- 2) association with clinical deterioration (such as a significant decline in performance status).

### **Confirmatory Measurement/Duration of Response**

#### **Confirmation**

To be assigned a status of PR or CR, changes in tumor measurements must be confirmed by repeat assessments that will be performed no less than 4 weeks after the criteria for response are first met. In the case of SD, follow-up measurements must have met the SD criteria at least once after study entry at a minimum interval of not less than 6 weeks.

#### **Duration of Overall Response**

The duration of overall response is measured from the time measurement criteria are met for CR or PR (whichever is first recorded) until the first date that recurrent or progressive disease is objectively documented (taking as reference for progressive disease the smallest measurements recorded since the treatment started).

The duration of overall CR is measured from the time measurement criteria are first met for CR until the first date that recurrent disease is objectively documented.

### **Duration of Stable Disease**

Stable disease is measured from the start of the treatment until the criteria for progression are met, taking as reference the smallest measurements recorded since the treatment started.

### **1.7.13 REMOVAL OF PATIENTS FROM STUDY/OFF STUDY CRITERIA**

In the absence of treatment delays due to adverse events, treatment may continue up to 109 weeks until one or more of the following criteria applies:

- a. Disease progression/relapse during active treatment, defined per modified RECIST v1.1 criteria
- b. Intercurrent illness that prevents further administration of treatment
- c. Unacceptable adverse event(s)
- d. In the event of any drug-related life-threatening toxicity or laboratory abnormality the patient will be withdrawn from further treatment
- e. Patient decides to withdraw from the study
- f. Non-compliance with treatment plan as per investigator discretion
- g. General or specific changes in the patient's condition render the patient unacceptable for further treatment in the judgment of the investigator
- h. Protocol violation - any patient found to have entered this study in violation of the protocol might be discontinued from the study at the discretion of the Principal Investigator.

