### **1.7.7 Dose Modifications and Withholding**

As toxicity of these agents is largely non-overlapping, management of toxicity is dependent on which agent is more likely to have resulted in the toxicity. Vertigo, somnolence, and circumoral paresthesia should be attributed to trigriluzole. Immune-related adverse events should be attributed to the anti- PD-1 antibody. Refer to agent-specific management instructions below for dose modifications and holdings.

*Overlapping toxicities of trigriluzole and anti- PD-1 antibody include fatigue, asthenia, nausea, dizziness, diarrhea, anorexia and liver injury. When these toxicities occur, both drugs should be held until toxicity resolves to grade 0-1.*

Study therapy (both agents) may be held for up to 6 consecutive weeks. Subjects who are not able to resume at least 1 study drug within a period of 6 weeks should be removed from the active treatment phase of the study and begin follow-up procedures.

Dosing interruptions are permitted in the case of medical / surgical events or logistical reasons not related to study therapy (e.g., elective surgery, unrelated medical events, patient vacation, and/or holidays). Missed doses should be omitted, not delayed. Subjects should be placed back on study therapy within 3 weeks of the scheduled interruption, unless otherwise discussed with the study PI or co-PI. The reason for interruption should be documented in the patient's study record. Tumor assessments should continue per the study calendar even if study medication was missed.

Delays due to holidays, weekends and bad weather will be permitted and will not be counted as a protocol violation, and efforts will be made to get the patient back on the original schedule so that assessments are uniform across subjects. If correlative samples are collected and the scheduled treatment that day is delayed/held for any reason, there is no need to re-collect correlative samples.

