### **Trigriluzole**

**Grade 3-4 Toxicity.** Any Grade 3 or 4 adverse event thought to be related (possibly, probably, or definitely) to trigriluzole will require the dose to be held until the event recovers to Grade 1 or less. When therapy resumes, the dose must be reduced by one level. If the adverse event does not improve to Grade 0-1 within 4 weeks of holding trigriluzole, the patient will be removed from the study.

**Grade 1-2 Toxicity.** Grade 1-2 adverse events do not require dose adjustment, except if the patient/physician considers them to be serious or intolerable—in this case, the dose may be reduced by one level as per the table below at the discretion of the treating investigator. An example is grade 1 dizziness that the patient finds intolerable.

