### Pembrolizumab and Nivolumab Dose Modifications

No dose reductions of pembrolizumab or nivolumab are allowed. PD-1 inhibitor must be withheld (not delayed) for drug-related toxicities

Adverse events (both non-serious and serious) associated with PD-1 inhibitor exposure may represent an immunologic etiology. These adverse events may occur shortly after the first dose or several months after the last dose of treatment. For suspected immune-mediated adverse reactions, ensure adequate evaluation to confirm etiology or exclude other causes.

**Grade 3-4 toxicity.** For Grade 3-4 immune-related adverse event (irAE) related to PD-1 inhibitor, withhold PD-1 inhibitor and if indicated, administer corticosteroids as per immune related adverse event guidelines. Upon improvement to Grade 1 or less, initiate corticosteroid taper and continue to taper over at least 4 weeks. Resume PD-1 inhibitor when the adverse reaction remains at Grade 1 or less following corticosteroid taper.

Permanently discontinue PD-1 inhibitor for any Grade 3 immune-mediated adverse reaction that recurs and for any life-threatening immune-mediated adverse reaction. If steroids are indicated longer than 8 weeks, the subject must discontinue treatment with PD-1 inhibitor.

Upon improvement to Grade 1 or less, the subject may resume treatment. The PD-1 inhibitor dose should be skipped (not delayed) and treatment should resume at the next scheduled timepoint.

If the toxicity is liver-related, trigriluzole must also be held (see above). Otherwise, PD-1 inhibitor therapy may be continued at the discretion of the treating investigator.

**Grade 3-4 toxicity.** For Grade 3-4 toxicity that is treatment-emergent and but not an irAE, (examples: fatigue, nausea), PD-1 inhibitor will be held until improvement of toxicity to a Grade 0-1.

**Grade 1-2 Toxicity.** Grade 1-2 adverse events do not require dose adjustment, except if the patient/physician considers them to be serious or intolerable—in this case, the PD-1 inhibitor may be held at the discretion of the treating investigator. An example is grade 2 fatigue.

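### Section 1.7.13(d) ends treatment after any drug-related life-threatening toxicity, but three holding rules in Section 1.7.7 make no exception for such events

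*Combined protocol and SAP*

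**What the plan says.** Section 1.7.13 lists the reasons for ending treatment. Criterion d reads: "In the event of any drug-related life-threatening toxicity or laboratory abnormality the patient will be withdrawn from further treatment". It draws no distinction by drug and leaves no discretion.

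Section 1.7.7 sets the holding and dose-modification rules:

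- **Trigriluzole, Grade 3-4.** "Any Grade 3 or 4 adverse event thought to be related (possibly, probably, or definitely) to trigriluzole will require the dose to be held" until recovery to Grade 1 or less. Then: "When therapy resumes, the dose must be reduced by one level". The patient is removed only if the event has not improved to Grade 0-1 within 4 weeks of holding.
- **PD-1 inhibitor, Grade 3-4, not immune-related.** "PD-1 inhibitor will be held until improvement of toxicity to a Grade 0-1".
- **Overlapping toxicities (a list that includes liver injury).** "When these toxicities occur, both drugs should be held until toxicity resolves to grade 0-1". No grade limit is given.
- **PD-1 inhibitor, Grade 3-4, immune-related.** "For Grade 3-4 immune-related adverse event (irAE) related to PD-1 inhibitor, withhold PD-1 inhibitor and if indicated, administer corticosteroids", and later "Resume PD-1 inhibitor when the adverse reaction remains at Grade 1 or less following corticosteroid taper". The next paragraph adds: "Permanently discontinue PD-1 inhibitor for any Grade 3 immune-mediated adverse reaction that recurs and for any life-threatening immune-mediated adverse reaction".

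Section 1.7.11 grades events by CTCAE version 4.0. Its definition of a serious adverse event describes life-threatening as an immediate risk of dying from the reaction and does not tie the term to a grade.

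**The concern.** Criterion d is triggered by severity. The first three rules above are triggered by grade or by type of toxicity, and they lead back to treatment once the event has resolved. A life-threatening, drug-related event that the patient survives can meet both sets of conditions. What happens next then depends on which section the treating investigator consults.

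The first issue is patient safety: whether a patient is exposed again to a drug judged related to a life-threatening event. The second is the data. Exposure and safety follow-up on treatment after the event would differ between patients with the same history. So could time to treatment failure, a secondary endpoint listed in Sections 1.1.3 and 6.1.

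**Working it through.** No arithmetic applies. The check compares the two sections for each kind of drug-related, life-threatening event that is not fatal and recovers. It assumes only that such an event is graded 3 or 4.

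1. **Related to trigriluzole, recovered to Grade 1 within 4 weeks.** Section 1.7.13(d) withdraws the patient. Section 1.7.7 holds the drug and restarts it one level lower. Its own removal trigger is failure to improve in time, not severity, so it is not met. The instructions are opposite. One limit: in Table 5 the first reduction for Cohort -1 is discontinuation, so there trigriluzole stops under either section. In Cohorts 1 to 4 the first reduction is a lower dose.

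2. **Related to the PD-1 inhibitor, not immune-related.** Section 1.7.13(d) withdraws the patient. Section 1.7.7 holds the PD-1 inhibitor until Grade 0-1. Resumption is implied by the wording of the hold rather than spelled out, but no exception is made. The instructions conflict.

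3. **On the overlapping list.** Section 1.7.13(d) withdraws the patient. Section 1.7.7 holds both drugs until Grade 0-1. The same section allows both agents to be held for up to 6 consecutive weeks and removes the patient from active treatment only if neither can be resumed. Removal again depends on time, not severity. The instructions conflict.

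4. **Immune-mediated.** Section 1.7.7 permanently discontinues the PD-1 inhibitor, and Section 1.7.13(d) ends treatment. For the PD-1 inhibitor they agree. They differ in scope: Section 1.7.7 requires trigriluzole to be held when the toxicity is liver-related and is otherwise silent on that drug, whereas Section 1.7.13(d) ends treatment as a whole. An immune-mediated liver injury falls under this case and case 3 together.

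5. **A Grade 4 laboratory value without immediate risk of death.** Section 1.7.7 applies by grade. Whether Section 1.7.13(d) applies cannot be determined, because the protocol does not link the term to a grade. This is an ambiguity, not a proven contradiction.

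**Effect on the analyses.** Section 6.1 counts a related Grade 3 or higher event in the evaluation period as a DLT, apart from the stated amylase and lipase exception. That definition does not ask whether treatment continued. Exposure before the event is the same under either instruction, and only what follows it differs. Time to treatment failure is listed but not defined, so an effect on it requires that withdrawal be counted as failure.

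**The case against.** The best defence is that the sections work at different levels. Criterion d is a study-wide reason for ending treatment, and the trigriluzole rule sets the dose only if treatment resumes. On that reading criterion d removes the life-threatening cases first, Section 1.7.7 governs the rest, and all that is missing is a cross-reference.

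This is a possible reading, but the protocol does not state it. No precedence clause exists. Section 1.7.7 sends the reader to the agent-specific instructions, and those contain their own removal rule, based on time to recovery. The PD-1 inhibitor text makes an express exception for life-threatening immune-mediated reactions. The absence of one from the other three rules therefore leaves real doubt.

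Two broader readings do fail:

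- A reader might infer from the instruction to resume after the corticosteroid taper that the PD-1 inhibitor may be restarted after a life-threatening immune-mediated reaction. The paragraph that follows rules this out.
- A reader might infer that every related Grade 4 event is caught by both sections. The documents do not equate Grade 4 with life-threatening.

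**Conclusion.** The contradiction stands for life-threatening drug-related events under three rules of Section 1.7.7: trigriluzole-related, PD-1-related but not immune-related, and overlapping toxicities. For immune-mediated reactions only the handling of trigriluzole is unclear. For Grade 4 laboratory values the scope of criterion d is unclear.

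The size cannot be put as a number, because the documents give no rate of such events. No sample size or power figure depends on it.

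Because cohorts are of 3, a reader might infer that one such event puts a third of a dose level's exposure data at stake. It does not: exposure up to the event is kept, and only that patient's later exposure differs. A reader might also infer that the MTD would shift. The DLT definition gives no support for that, since it counts the event whether or not treatment continues.

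The point therefore rests on patient safety and consistent conduct, with a conditional effect on a secondary endpoint that is analysed descriptively. It is worth correcting for those reasons.

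**What to change.** Reconcile Section 1.7.13(d) with Section 1.7.7: the overlapping-toxicity rule, the trigriluzole Grade 3-4 rule and the PD-1 inhibitor rules. The amended text should:

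- give each type of event one instruction, or state which section prevails;
- say whether the instruction applies to one drug or both, including what happens to trigriluzole after a life-threatening immune-mediated reaction;
- state how life-threatening maps to CTCAE grade, and whether a Grade 4 laboratory value alone triggers criterion d.

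Which clinical rule to adopt is for the sponsor-investigator, and no position is taken here. The cost is amendment wording, with no change to sample size or to the escalation design.

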### **1.8 Primary Specimen Collection**

#### **Collection of Blood and Tumor Tissue for Laboratory Correlative Studies**

Tumor biopsies and blood samples will be performed for correlative analyses to measure changes in the tumor microenvironment and peripheral blood including, but not limited to, the following categories:

- Immune cell phenotypes and gene expression
- Angiogenesis markers
- Metabolic effector molecules
- Exosome biogenesis
- Pharmacokinetic (PK)

Please refer to Lab Manual for analysis plan for laboratory correlative assays.

If correlative samples are collected and the scheduled treatment that day is delayed/held for any reason, there is no need to re-collect correlative samples.

### **Tumor Sampling**

- Archival tissue (a block or 6-10 unstained slides) will be obtained for all subjects, when available.
- Tumor biopsies for research purposes are optional, but strongly encouraged, at Baseline/Week -2 (anytime pre-treatment, untimed sample), Week 1 (pre-infusion, untimed sample) and Week 7 (pre-infusion, untimed sample).
- Regarding the method of biopsy, excisional biopsy or punch biopsy is preferred over core needle biopsy for purposes of tissue sampling for correlative studies. An optimal size is 15 x 15 mm, but 5 mm x 5 mm is also useful, and there is no minimum size that is required. If a core needle biopsy is performed, 1-3 cm of core is required. If the lesion is < 2 cm in longest diameter and it is a RECIST target lesion, care should be taken to ensure that the overall size of the target lesion is not affected by the tissue sampling. In this case, a small excisional biopsy or core biopsy should be performed.
- Refer to the Lab Manual for more details on collection, processing and storage.

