### **1.7.9 Supportive Care Guidelines**

Patients are allowed to receive full supportive care therapies concomitantly during the study. Supportive medications may be used to treat fever, rash, diarrhea and other common adverse events.

Management of infusion reactions should follow the site's SOPs for infusion or hypersensitivity reactions. Premedications are not required but are allowed for patients with previous infusion reaction.

Radiation therapy may be delivered to a non-target lesion and the patient may remain on-study. For example, radiation therapy may be given to patients with isolated CNS progression.

Surgery or radiation therapy may be performed to palliate a tumor if it is not a target lesion for tumor assessment. If a target lesion requires surgery, the patient should be removed from active treatment due to clinical progressive disease.

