### RECIST Response Categories

#### Evaluation of Target Lesions

Complete Response (CR):	Disappearance of all target lesions
Partial Response (PR):	At least a 30% decrease in the sum of the longest diameter (LD) of target lesions, taking as reference the baseline sum LD.
Progressive Disease (PD):	At least a 20% increase in the sum of the LD of target lesions, taking as reference the smallest sum LD recorded since the treatment started or the appearance of one or more new lesions. In addition to the relative increase of 20%, the sum must also demonstrate an absolute increase of at least 5 mm. (Note: the appearance of one or more new lesions is also considered progression).
Stable Disease (SD):	Neither sufficient shrinkage to qualify for PR nor sufficient increase to qualify for PD, taking as reference the smallest sum LD since the treatment started.

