## **III. Collection of fresh tumor tissue**

- a. Method of biopsy: Excisional biopsy or punch biopsy is preferred over core needle biopsy for purposes of tissue sampling for correlative studies. An optimal size is 15 x 15 mm, but 5 mm x 5 mm is also acceptable. There is no minimum size that is required. If a core needle biopsy is performed, 1-3 cm of core is recommended. If the lesion is < 2 cm in longest diameter and it is a RECIST target lesion, care should be taken to ensure that the overall size of the target lesion is not affected by the tissue sampling. In this case, a small excisional biopsy or core biopsy should be performed.
- b. The RCINJ Biospecimen Repository Service (BRS) will process, label and store the tissues samples.
- c. Fresh tumor tissue for Western blotting will be collected by biopsy and immersed (completely) in sterile cold (2-7°C) RPMI in a sterile specimen cup (for example, VWR catalog# 15704-088) on ice.
- d. Fresh tumor tissue for murine experiments will be collected in sterile cold (2-7°C) RPMI in a sterile 50 ml centrifuge tube.
- e. The specimen cup or centrifuge tube will be labeled with the patient ID, date, and time of tumor tissue collection.
- f. The sample will be immediately transported on ice from the collection site to the BRS laboratory.
- g. Tissue processing should be performed as soon as possible after tissue collection/receipt (maximum time from tissue acquisition and processing should be no more than 3 hours).

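### Research biopsies may be taken from RECIST target lesions after the baseline scan, with no size safeguard at 2 cm or more and no rule for scoring a sampled lesion

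*Combined protocol and SAP*

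**What the plan says.** **Biopsy method and size.** Section 1.8 (Tumor Sampling) states that "excisional biopsy or punch biopsy is preferred over core needle biopsy for purposes of tissue sampling for correlative studies". On size it says "An optimal size is 15 x 15 mm, but 5 mm x 5 mm is also useful"; no minimum is required and no maximum is given. Appendix B, part III, repeats this in nearly the same terms. Neither place says that target lesions may not be sampled.

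**The safeguard.** It opens with a condition: "If the lesion is < 2 cm in longest diameter and it is a RECIST target lesion". It then asks that "care should be taken to ensure that the overall size of the target lesion is not affected by the tissue sampling", and ends: "In this case, a small excisional biopsy or core biopsy should be performed". There is no matching text for target lesions of 2 cm or more.

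**Timing.** Research biopsies are planned at Baseline, Week 1 and Week 7. Section 1.3.3 lets the baseline sample be taken at any point before therapy. Section 1.7.12 puts the baseline measurement within 4 weeks before treatment. Neither sets an order between the two. Tumor assessments follow at Week 7, Week 13 and later.

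**Scoring.** Section 1.7.12 defines partial response as "At least a 30% decrease in the sum of the longest diameter (LD) of target lesions", measured against the baseline sum. Progression is judged from the smallest sum on record and needs a rise of both 20% and 5 mm. Response is confirmed by a repeat assessment at least 4 weeks later. Section 6.1 counts anyone with one on-study tumor assessment as evaluable for response. None of these sections mentions a target lesion that has been biopsied.

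**The concern.** Response and progression are read from changes in the sum of target-lesion diameters. If tissue is cut from a target after the baseline scan, the sum falls for a reason unrelated to treatment, and the plan has no rule to separate the two.

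The situation is realistic. All measurable lesions become targets up to 2 per organ and 5 in total, and entry needs only one measurable lesion. In a subject with little disease, the only lesion accessible for biopsy may therefore be a target. Superficial lesions measured clinically can be targets, and they are also well suited to punch or excision.

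The endpoints exposed are ORR, duration of response, PFS and the other progression-based times, together with the responder and non-responder groups on which the correlative work in Section 6.1 is built. Progression also ends treatment under Section 1.7.13, so a nadir lowered by biopsy could affect a subject's time on study drug.

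**Working it through.** The plan gives no power or precision target for ORR, so there is no stated figure to reproduce. The check applies the plan's own response rules.

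**Inputs**
- Partial response: fall of at least 30% from the baseline sum (1.7.12).
- Progression: rise of at least 20% and at least 5 mm from the smallest sum (1.7.12).
- Biopsy dimension: 15 mm optimal, 5 mm also useful (1.8). The 10 mm row is an intermediate value added here.
- Total sample size: 12 to 27 (1.5 and 6.1).
- Worst-case assumption: the full biopsy dimension comes off the longest diameter, and the tumor does not otherwise change.

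**1. When tissue loss alone meets partial response**

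Percent change = -(mm lost) / (baseline sum), so the threshold is met when baseline sum ≤ mm lost / 0.30.

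| Loss of diameter | Largest baseline sum meeting -30% |
|---|---|
| 15 mm | 15 / 0.30 = 50 mm |
| 10 mm | 10 / 0.30 = 33.3 mm |
| 5 mm | 5 / 0.30 = 16.7 mm |

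For a 15 mm loss:
- sum 20 mm: -75%
- sum 30 mm: -50%
- sum 40 mm: -37.5%
- sum 50 mm: -30%
- sum 51 mm: -29.4%, not a response
- sum 60 mm: -25%, not a response

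A 5 mm loss reaches 30% only at sums of 16.7 mm or less. Every target is then under 2 cm, so the care clause applies. The clearly unguarded range for one 15 mm sample is a sum of 20 to 50 mm that includes a target of at least 2 cm.

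**2. Larger sums**

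The true shrinkage still needed after a 15 mm loss is (0.30 × sum - 15) / sum. This gives 5% at 60 mm, 10% at 75 mm and 15% at 100 mm, in place of 30%.

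**3. Confirmation**

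The repeat assessment measures the same shortened lesion. A fall caused by excision is therefore confirmed unless the lesion regrows in the meantime.

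**4. Effect on progression**

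Take a single 30 mm lesion. Uncut, progression needs 30 × 1.20 = 36 mm. Cut to 15 mm, 20% is only 3 mm, so the 5 mm minimum governs and progression is met at 15 + 5 = 20 mm, below the original size.

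**5. Effect on ORR**

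One false response adds 1/27 = 3.7 points to 1/12 = 8.3 points, if all planned subjects are in the denominator. The plan asks for 90% intervals without naming a method; exact (Clopper-Pearson) intervals are used here. Starting counts are near 20%, the low end of the 20–45% anti-PD-1 range in Section 1.4.7.

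| N | Before | With one false response |
|---|---|---|
| 12 | 2/12 = 16.7% (3.0 to 43.8) | 3/12 = 25.0% (7.2 to 52.7) |
| 27 | 5/27 = 18.5% (7.6 to 35.1) | 6/27 = 22.2% (10.1 to 39.2) |

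**6. Position of the three biopsies**

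Week 1 comes after the lead-in, so it always falls between the baseline and Week 7 scans. The Baseline biopsy may fall on either side of the baseline scan. The Week 7 biopsy may fall on either side of the Week 7 scan.

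**The case against.** The strongest defense is that the plan means to protect target lesions and that the damaging case is narrow.

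- *Size.* A reader might infer that target lesions may be cut away up to 15 x 15 mm. The documents do not say so. That figure is an optimum in the general biopsy text, not a limit and not an instruction about targets. Removal of a target is permitted by silence, not directed.
- *Small targets.* A reader might also take complete excision of a target under 2 cm as allowed. The care clause goes against that, because its stated aim is to leave lesion size alone. What stands is the ambiguity of pairing that aim with an excision.
- *Conflict with Section 1.7.9.* That section says "If a target lesion requires surgery, the patient should be removed from active treatment due to clinical progressive disease", and a reader might see a contradiction. The context is palliation and a lesion that needs surgery for clinical reasons. The section is silent on research biopsy, so the two do not contradict each other, although its intended reach could be stated.
- *Other protection.* Target lesions are also to be chosen for how reliably they can be re-measured, which counts against a lesion due for substantial excision. This helps, but it does not mention biopsy.
- *Likely size of samples.* Appendix B expects many samples to be small and has an allocation class below 5 x 5 mm. This makes a full 15 mm loss less likely, but it does not rule one out.
- *Stakes.* Section 1.8, the study calendars and Appendix B make research biopsies optional. ORR is secondary and descriptive, no dose decision uses it, and an 8.3-point shift at N = 12 lies well inside the 90% interval. All of this stands and limits the point. Section 4.1.8 calls the biopsies mandatory, however, and that separate conflict needs reconciling.

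**Conclusion.** The point holds as a gap in the plan. Target lesions may be sampled after the baseline scan with excision or punch preferred. The explicit size safeguard stops at 2 cm and is unclear below it. No rule says how a sampled target is scored.

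The worst case is a false partial response at baseline sums of 50 mm or less. It requires the whole 15 mm to be lost along the longest diameter with no other change. The same loss can bring progression forward, to 20 mm instead of 36 mm for a 30 mm lesion cut to 15 mm. Each false response is worth 3.7 to 8.3 points of ORR.

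The documents give no basis for estimating how many subjects would be affected, so they do not support a conclusion that the reported ORR will be inflated. Only secondary, descriptive endpoints and the responder groupings are exposed; MTD/RP2D is untouched. This is a worthwhile, inexpensive improvement, not a threat to the main purpose of the trial.

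**What to change.** **Section 1.8 and Appendix B, part III.** Extend the size safeguard to all target lesions. Direct the Baseline, Week 1 and Week 7 research biopsies to non-target lesions where one is available. Record which lesion was sampled.

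**Section 1.7.12, Target Lesions.** Allow a planned biopsy site to be left out of the target set when another measurable lesion exists. The present text takes in all measurable lesions up to the cap, so it has to change for this to work.

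**If a target must be sampled.** Take the Baseline sample before the baseline scan and the Week 7 sample after the Week 7 scan. At Week 1, use a method that leaves the measured diameter unchanged, or omit the optional sample. The Week 7 order protects only that scan; Week 13 and later depend on the scoring rule below.

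**Section 1.7.12 (response rules) and Section 6.1 (evaluable for response).** State that a target whose diameter was reduced by biopsy is dropped from both the baseline and the follow-up sums. State that a subject with no remaining target is not evaluable for response. Report ORR with and without such subjects.

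**Cost.** Wording changes in four places. Some optional samples will be smaller or missing in subjects with a single accessible lesion, and a few subjects may become not evaluable for response.
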